6.2.2 Secondary Endpoints

Standard statistical methods will be employed to analyse the data. It is anticipated that the following techniques may be used: descriptive statistics, t-test, paired t-test, analysis of variance, Fisher exact test, Chi-square test, and graphical displays. Assumptions of normality will be tested with the Shapiro-Wilk test. Assumptions of homogeneity of variance will be tested with Levene's test. If the distributional assumptions are (severely) violated, non-parametric techniques, such as Mann-Whitney's test will be employed.

All tests will be declared statistically significant if the calculated p-value is less or equal to 0.05. All tests will appear as two-sided p-values. Summary statistics will consist of numbers and percentages of responses in each category for discrete measure, and of means, medians, standard deviation, 95% confidence interval, minimum, maximum for continuous measures, and will be presented per treatment group.

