2.1 Primary objective

- The primary objective of this study is to compare clinical outcomes at two years following surgery between FA TKA and MA TKA. The primary outcome measure for this study is the Forgotten Joint Score (FJS) at two years after surgery. The null hypothesis is that there is no difference in functional scores at two years following surgery between patients undergoing MA TKA (control group) versus FA TKA (investigation group). The hypothesis is that outcome measures obtained at two years after surgery in patients undergoing FA TKA are not achievable using MA TKA. Further PROMs will be used to further assess clinical outcomes including Forgotten Joint Score (FJS), Oxford Knee Score (OKS), Knee injury and osteoarthritis outcome Junior score (KOOS Jr), VAS Pain, and Kujala scores preoperatively and postoperatively at 3 months, 1 year and 2 years. Also health-related quality of life will be measured using European Quality of Life questionnaire with 5 dimensions for adults (EQ-5D-5L) preoperatively and postoperatively at 3 months, 1 year and 2 years. Range of movement (degrees) in knee joint during inpatient admission and postoperatively at 6 weeks, 3 months, 1 year and 2 years.

2.2 Secondary objectives The secondary objectives of the study are:

- Determine lower limb alignment achieved with both alignment techniques. Lower limb alignment as assessed using standing long leg x-rays performed postoperatively at 3 months. Measurements of the hip-knee-angle (HKA), medial proximal tibial angle (MPTA) and lateral distal femoral angle (LDFA). Also evidence of imbalance with implant lift off will be measured.

- Determine if there are any differences in analgesic requirements based on alignment method used. Analgesia requirements during inpatient admission and postoperatively at 6 weeks, 3 months, 1 year and 2 years will be measured.
- Determine whether alignment method utilized has an effect on the sagittal stability of the TKA. Assessment of sagittal stability at Preop, 3 months, 1 year and 2 years will be undertaken with an arthrometer “Lachmeter”.
- Determine whether alignment method utilized has an effect on functional outcomes. This will be assessed by a combination of
 - Maximum voluntary isometric force using a hand-held dynamometer at Preop, 3 months, 1 year and 2 years.
 - Sit to stand values as measure of function at Preop, 3 months, 1 year and 2 years.

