3.7 Surgical Intervention: MA vs. FA TKA

All patients undergoing TKA will undergo preoperative CT scan of the leg to establish the extent of the disease process, determine bone resection, and plan implant sizing and positioning. The preoperative CT scan will be used to create individualized plans for achieving mechanical and kinematic alignment and stored within the robotic program that is used during the operative procedure. This will ensure that all implants and equipment for achieving either mechanical alignment or functional alignment are ready and available for use in theatre. These

plans will provide the initial point from which functional alignment will be achieved.

Following informed consent and randomisation into one of the two treatment groups, patients will undergo robotic-arm assisted TKA by one of the participating surgeons. Surgery in both groups will be undertaken through the standard anteromedial arthrotomy with positioning of reference pins in the femur and tibia for registration of the hip centre, ankle position and limb alignment. The femur will be prepared first in all operations. Cruciate retaining technique will be used in both groups. Interoperative requirement for a more constrained implant will result in exclusion from the study.

In MA TKA, tibial and femoral osteotomies in the coronal plane will be planned perpendicular to the tibial and femoral mechanical axes respectively to achieve neutral overall alignment. Soft tissue balance will be assessed and minor adjustments to bony alignment made to balance the knees with a maximal adjustment of two degrees valgus and two degrees varus of coronal alignment from neutral. Femoral rotation will be planned to surgical epicondylar axis and adjustments to rotation made to allow equal flexion and extension balance (to within 1mm). If balance can not be achieved within these boundaries then soft tissue release will be undertaken.

In the sagittal plane, 0-3 degrees of posterior tibial slope and 0-5 degrees of femoral component flexion will be used to optimise implant sizing whilst preventing notching. In the axial plane, the tibial component aligned to Akagi's line, which connects the medial border of the patellar tendon attachment to the middle of the posterior cruciate ligament.

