In kFA TKA, femoral and tibial osteotomies will be planned for equal bony resections from the femoral condyles to replicate the patients anatomy. In the coronal plane, the distal femoral resection will be 6.5mm from the subchondral bone of both medial and lateral condyles, with compensation for wear by adjusting the resection by 1-3mm. In the proximal tibia, there will be 7mm of resection from the subchondral bone from both the medial and lateral tibial plateau. In the sagittal plane, resection angle will be determined intraoperatively to closely match the native femoral flexion and tibial slope. In the axial plane, posterior femoral resection will be 6.5mm from the subchondral bone of both medial and lateral posterior condyles. Tibial rotation will be aligned to Akagi's line. Adjustments will be made to bony alignment to balance soft tissues within the boundaries of six degrees varus and three degrees valgus Hip-Knee-Ankle (HKA) alignment. Femoral component alignment will be limited to six degrees of valgus and three degrees of varus in the coronal plane. Tibial alignment will be limited to six degrees of varus and three degrees of valgus in the coronal plane. Combined flexion of the components will be limited to ten degrees of flexion. Only if balance can not be achieved within these boundaries will soft tissue release be undertaken.

In both groups, polyethylene thickness will be selected to maximise range of motion whilst avoiding hyperextension and ligament laxity. Tibial depth will be adjusted to maintain insert thickness between 9 and 14mm. Any TKA requiring a 16 mm or greater polyethylene insert thickness will be excluded from the study.

Patients in both groups will undergo the same inpatient and outpatient postoperative rehabilitation programme. Intra-operative data will be recorded using the surgical data form (Appendix 19.7). The only difference between the two treatment groups is that the control group will undergo MA TKA and the investigation group will undergo FA TKA.

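### Section 6.2.2 lets a failed variance test lead to Mann-Whitney, which does not correct unequal variance and leaves the alignment angles without a between-arm difference in degrees

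*Combined protocol and SAP*

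**What the plan says.** Section 6.2.2 introduces its list of methods, which includes the t-test and analysis of variance, with "It is anticipated that the following techniques may be used". It then sets two pre-tests: "Assumptions of normality will be tested with the Shapiro-Wilk test" and "Assumptions of homogeneity of variance will be tested with Levene's test". The consequence of failing them is "If the distributional assumptions are (severely) violated, non-parametric techniques, such as Mann-Whitney's test will be employed". The significance rule is "All tests will be declared statistically significant if the calculated p-value is less or equal to 0.05", with two-sided p-values. Continuous measures are to be summarised by mean, median, SD and 95% CI within each treatment group. No between-arm effect measure is named for any secondary endpoint.

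The alignment outcomes are HKA, MPTA and LDFA, read from standing long-leg x-rays at 3 months (section 2.2). Section 3.7 limits coronal alignment differently by arm. The control arm is balanced "with a maximal adjustment of two degrees valgus and two degrees varus of coronal alignment from neutral", and the investigation arm "within the boundaries of six degrees varus and three degrees valgus Hip-Knee-Ankle (HKA) alignment". The limit tables in Appendix 19.9 repeat this for HKA, tibial coronal and femoral coronal position.

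**The concern.** There are three difficulties.

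- **The choice of test depends on the data.** It turns on the word *severely*, for which no threshold is given. Two analysts could take the same data to different tests.
- **The remedy does not match one of its triggers.** Mann-Whitney is a reasonable response to non-normality. It does not correct for unequal variance: when spreads differ, it no longer tests equality of means. Welch's t-test handles unequal variance directly and is not named.
- **This trial is likely to meet that trigger.** The two arms are allowed coronal windows of very different width, and the angles affected are the listed radiological outcomes.

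At stake is mainly interpretation. Readers will want to know by how many degrees the arms differ, and with what precision. After a switch they would see a mean for each arm beside a p-value that does not test the difference between those means, and no planned interval for that difference. Endpoints could also end up on different scales if some switch and others do not.

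**Working it through.** **1. Arm size.** This is the only design figure needed. Section 3.5 gives 100 enrolled 1:1, and section 6.1 a 10% drop-out: 100 × (1 − 0.10) = 90, and 90 / 2 = 45 per arm, as section 3.5 states. The plan gives no figure for the alignment endpoints. The checks below use 45 and 50 per arm.

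**2. Width of the windows (section 3.7, Appendix 19.9).** For HKA and tibial coronal angle, control is 2 + 2 = 4 degrees and investigation 6 + 3 = 9 degrees. For the femoral coronal angle, control is again 2 + 2 = 4 and investigation 3 + 6 = 9. The ratio is 9 / 4 = 2.25.

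**3. Spread this could imply.** No SD for any angle is given, so these are assumptions.

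- Knees fill the window evenly: SD = width / √12, so 4 / 3.464 = 1.15 and 9 / 3.464 = 2.60.
- Underlying alignment is normal with mean 2 and SD 3, and knees beyond a limit are set at it: SDs 1.42 and 2.63, means 0.93 and 1.93.
- Functional-arm knees barely use the extra room: SDs 0.88 and 0.99.

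**4. Rejection rate when true means are equal** (two-sided 0.05). There were 20,000 simulated trials per case. Means were made equal by recentring, to isolate the effect of spread. Ranges cover 45 and 50 per arm.

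| Assumed case | SDs | Levene rejects | Mann-Whitney | Welch |
|---|---|---|---|---|
| Even fill | 1.15, 2.60 | over 99% | 6.5-6.7% | 4.8-5.3% |
| Normal, same SDs | 1.15, 2.60 | over 99% | 6.1% | 4.9-5.2% |
| Clamped at limits | 1.42, 2.63 | 98-99% | 7.0% | 5.0-5.1% |
| Clamped, plus 1 degree x-ray error | 1.74, 2.82 | 90-94% | 5.6-5.8% | 5.1-5.2% |
| Wider window barely used | 0.88, 0.99 | 9-10% | 4.8-5.1% | 4.9-5.1% |

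The Monte Carlo standard error near 7% is √(0.07 × 0.93 / 20,000) = 0.18 percentage points.

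The full rule was also run on 3,000 trials per case: any Shapiro-Wilk or Levene p ≤ 0.05 leads to Mann-Whitney, otherwise the t-test. It gave 5.8-7.4% in the first three rows, 5.5-5.8% with x-ray error and 5.4% in the last row. Its standard error near 7% is √(0.07 × 0.93 / 3,000) = 0.47 points, so the 7.4% is compatible with the 7.0% above.

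The ordinary pooled t-test also stayed at 5.0-5.4% in all five cases, because the arms are equal in size.

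One stress case did much worse: a strongly right-skewed functional arm gave 26-28% for Mann-Whitney against 5.6-5.8% for Welch. That distribution is not confined to the protocol limits, so it is not used in the conclusion.

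**5. Power for a real difference.** In the clamped case without recentring, the difference in means is 1.93 − 0.93 = 1.00 degree. Mann-Whitney rejects in 53-56% and Welch in 60-64%.

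**The case against.** The case for leaving the text alone has real weight.

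- **Limits cap the range; they do not set the SD.** A reader might infer that the arms' limits force unequal variances. The documents do not support that. Functional-arm knees may cluster inside the narrow window, and in that case Levene seldom rejects. This stands.
- **The limits apply to the robotic plan, while the endpoint is a 3-month x-ray.** Measurement error dilutes the difference in spread and brings the error rate down. This stands, and is why the lower figures in the table matter.
- **The switch is not automatic.** The text says techniques may be used, requires severe violation, and offers Mann-Whitney as an example. The listed t-test is not said to be the pooled version. This stands as a reading. It also means that the analysis is not fixed, which is half of the point.
- **A reader might call Mann-Whitney invalid here.** Section 6.2.2 states no mean-difference target, and Mann-Whitney remains a valid test that two distributions are identical. The fair statement is that it does not test or estimate the difference in means.
- **False positives matter little for component angles.** Section 1 reports a mean tibia of 4 degrees varus with the kinematic plan, against a control limit of 2 degrees varus, so a shift is largely designed in. This stands. It moves the weight from error rates to estimation, which is where the plan is silent.
- **For patient-reported scores**, frequent failure of Shapiro-Wilk under a ceiling might suggest that the rule harms those endpoints. No loss of error control or power from Mann-Whitney has been shown there. The argument for them is only a test known in advance and a common scale.

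**Conclusion.** The point holds, and it is minor. Section 6.2.2 makes unequal variance a possible reason for Mann-Whitney, sets no threshold, and plans no between-arm estimate. The 4-degree and 9-degree windows make unequal spread likely, not certain, for HKA, MPTA and LDFA.

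If the switch occurs, the type I error as a test of means is about 5.5-7%, or about 5.5-6% with x-ray error, against about 5% for Welch. In the clamped case, power falls short of Welch's by roughly 60 − 53 = 7 to 64 − 56 = 8 percentage points. These figures rest on assumed angle distributions, on 45-50 per arm, and on reading any pre-test p ≤ 0.05 as a violation. They do not support a claim of serious inflation.

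The larger cost is an alignment result without a between-arm difference and interval in degrees. A reader might extend the concern to the primary endpoint. Section 6.2.1 has its own confidence-interval analysis for the FJS, and the pre-test rule is stated only under secondary endpoints, so the primary analysis is not affected.

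**What to change.** In section 6.2.2, delete the pre-test-and-switch rule for the alignment angles and the other continuous secondary endpoints, and fix one method. Suggested wording:

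> Continuous secondary endpoints will be compared between groups with Welch's t-test, two-sided at the 0.05 level. The between-group difference in means and its 95% confidence interval will be reported in the units of the measure. A Mann-Whitney test will be reported as a sensitivity analysis and labelled as such.

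Shapiro-Wilk and Levene results may still be shown as description, provided that they do not decide the method. The cost is a change of wording: no additional data, visits or patients are needed.

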6.3 Intention-to-treat population

The intention-to-treat (ITT) population is defined as all randomised patients assigned to either the mFA TKA or kFA TKA group, regardless of adherence with the entry criteria, regardless of the treatment they actually received, and regardless of subsequent withdrawal from treatment or deviations from the protocol. In the event that MA is converted to FA or vice versa intraoperatively, analysis will be performed using the ITT population and the treatment actually received by the patients. Intra-operative conversion from one method to another will however, be documented and presented/ published as part of the study.

In the event that there are errors in the randomization assignment, the analysis will be performed using the assigned treatment, not the treatment that the patient actually received. Any patient terminated early from the clinical trial will be included in the ITT population. All attempts will be made to collect complete follow-up evaluations for these patients despite study exit. These patients will be included in the analysis using univariate or multivariate-imputation methods.

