6.2 Endpoint Analysis

6.2.1 Primary Endpoint

The analysis of the per-protocol population will be considered the primary analysis. The differences

between the MA TKA and FA TKA groups will be analysed by calculating the difference from baseline, per patient, and a two-sided confidence interval for the difference between the changes from baseline will be calculated. This confidence interval will cover the true difference in the percentage change from baseline with a probability of 95%.

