6.4 Per-protocol population

The per-protocol population is defined as all patients who are randomised to MA TKA or FA TKA and complete the study according to the protocol.

In the event that there are errors in the randomisation assignment, the analysis will be performed using the treatment that the patient actually received, not the assigned treatment. Patients will be considered protocol violators if they do not meet the eligibility criteria as outlined in the protocol. Other reasons to be considered a protocol violator include, but are not limited to, protocol violations, and any actions that compromise the effectiveness of the treatment, such as receiving a secondary treatment. Protocol violators will not be considered as part of the per-protocol population and will be listed separately with the reason for their exclusion from the per-protocol population.

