19.8 Intraop Data Collection Form

Patient Details

RCT Patient ID- Height: cm Weight: kg BMI:

Gender: Male Female ASA Score _____ Total Knee Replacement: Left Right

Pre-Operative

ACL Intact: Yes **OR** No

Pre-Operative Plan – Femur (Preplanning page after surgeon review) **Size:** _____

Femoral Coronal Alignment: _____ ° Varus **OR** Valgus

Femoral Rotation to TEA: _____ ° Internal **OR** External

Femoral Rotation to PCA: _____ ° Internal **OR** External

Distal Femoral Resection: Lateral _____ mm Medial _____ mm

Post Femoral Resection: Lateral _____ mm Medial _____ mm

Femoral Flexion Angle: _____ ° Extension **OR** Flexion

Pre-Operative Plan – Tibia (Preplanning page after surgeon review) **Size:** _____

Tibial Alignment: _____ ° Varus **OR** Valgus

Tibial Rotation: _____ ° Internal **OR** External

Tibial Slope: _____ ° Anterior **OR** Posterior

Tibial Resection: Lateral _____ mm Medial _____ mm

Intra-Operative

Surgical Times (Please record in 24-hour format)

Surgery Start: :: **Implantation:** :: **Surgery Finish:** ::
 (Knife-to-skin) (Hour) (Mins) (Final implant placed) (Hour) (Mins) (Wound Closure) (Hour) (Mins)

Surgical Theory (Select one)

Mechanical Alignment **OR** Mechanical w/ Bony Release **OR** Functional Alignment

Initial Limb Alignment (Joint balancing page – ACL and osteophytes removed)

ROM: _____ ° TO _____ ° **Note:** Record hyperextension as a negative value.

Knee Alignment - Extension Without Stress: _____ ° Varus **OR** Valgus
Flexion Without Stress: _____ ° Varus **OR** Valgus

Maximum Gap Values: Extension Pose (5-15° flexion)

Maximal Varus: _____ ° Varus **OR** Valgus Lateral Gap: _____ mm

Maximal Valgus: _____ ° Varus **OR** Valgus Medial Gap: _____ mm

RCT Patient ID-

Maximum Gap Values: Flexion Pose (85-95° flexion)

Maximal Varus: _____ ° Varus **OR** Valgus

Lateral Gap: _____ mm

Maximal Valgus: _____ ° Varus **OR** Valgus

Medial Gap: _____ mm

Changes to Implant Position and order of changes:

Femoral Coronal: Y/N

Tibial Coronal: Y/N

Femoral Rotation: Y/N

Tibial Rotation: Y/N

Femoral Sagittal: Y/N

Tibial Slope: Y/N

Femoral AP Position: Y/N

Tibial Depth: Y/N

Femoral Depth: Y/N

Total number of changes: _____

Details of changes:

Final Intra-Op Plan

Final Plan – Femur **Size:** _____

Femoral Coronal Alignment: _____ ° Varus **OR** Valgus

Femoral Rotation to *TEA*: _____ ° Internal **OR** External

Femoral Rotation to *PCA*: _____ ° Internal **OR** External

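### Section 6.3 contradicts itself on which arm an intraoperatively converted knee is analysed in, so the plan secures no as-randomised comparison

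*Combined protocol and SAP*

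**What the plan says.** Section 6.3 speaks to three situations.

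- **Definition.** The ITT population is everyone randomised, "regardless of the treatment they actually received, and regardless of subsequent withdrawal from treatment or deviations from the protocol".
- **Intraoperative conversion between MA and FA.** The rule begins: "In the event that MA is converted to FA or vice versa intraoperatively, analysis will be performed using the ITT population and the treatment actually". Its main clause, given in full, is that "analysis will be performed using the ITT population and the treatment actually received by the patients". The next sentence adds: "Intra-operative conversion from one method to another will however, be documented and presented/ published as part of the study".
- **Error in the randomisation assignment.** Here "the analysis will be performed using the assigned treatment, not the treatment that the patient actually received".

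Two other sections bear on how much rests on this. Section 6.2.1 states: "The analysis of the per-protocol population will be considered the primary analysis". Section 6.4 limits that population to patients who complete the study as the protocol requires, removes protocol violators, and for assignment errors says that "the analysis will be performed using the treatment that the patient actually received, not the assigned treatment". Section 6.4 does not mention conversions by name.

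Section 2 describes the design as superiority. Section 5.1 relies on the ITT principle for patients who need PCL release.

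**The concern.** An analyst working from 6.3 cannot tell which arm a converted knee belongs to. The definition and the assignment-error rule point to the randomised arm; the conversion sentence points, at least in part, to the operation performed.

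Conversion is not a chance event. It is a decision taken during the operation by a surgeon who knows the allocation, so it may depend on features of the knee that also affect the Forgotten Joint Score (FJS). Regrouping on such a decision undoes randomisation for those patients. Because the primary analysis is per-protocol, the ITT analysis is where a reader would look for a comparison protected by randomisation.

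**Working it through.** **1. The rules in 6.3 side by side**

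| Situation | Grouping that 6.3 gives |
|---|---|
| General definition | Irrespective of treatment received |
| Assignment error | Assigned arm |
| Intraoperative conversion | ITT population *and* treatment received |

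In the last two rows the patient may have had the other arm's operation, but the instructions differ.

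**2. Possible meanings of the conversion sentence**

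- (a) The ITT set is grouped by operation received. The analysis is then as-treated for converted knees.
- (b) Two analyses are intended, one ITT and one as-treated. The ITT comparison survives, but nothing says which result counts if they differ.
- (c) A *not* was dropped before the reference to treatment received. The word *however* in the next sentence fits this, as do the definition and the assignment-error rule. The sentence then states the opposite of what was meant.

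The text does not settle which is right. All three need the same correction.

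**3. Whether another analysis preserves randomisation**

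None that is described does so. The per-protocol analysis (6.2.1, 6.4) removes violators and groups assignment errors as received.

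**4. Whether conversion could be selective**

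The allocation is disclosed to the Chief Investigator for planning (3.6), and the preoperative plan is built on it (19.9). Gaps are measured before the bone cuts (19.9). The limits differ by arm: hip-knee-ankle alignment of 2° varus to 2° valgus for control, and 6° varus to 3° valgus for FA (3.7, 19.9). A conversion would therefore be made knowing both the arm and the state of the knee.

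**5. Illustration of size**

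The plan gives no conversion rate, so it has no figure on this point to reproduce.

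From the documents: 45 completers per arm (3.5) and a target difference of 12 FJS points (6.1).

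Assumed: no true effect; a share *p* of knees in each arm scores *h* points lower; all such MA knees, and no others, are converted to FA. The SD is taken as the value at which 45 per arm gives 80% power for 12 points at alpha 0.05:

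- one-sided: 12 × √(45/2) / (1.645 + 0.842) = 22.9
- two-sided: 12 × √(45/2) / (1.960 + 0.842) = 20.3

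Neither SD is stated in the plan. Section 6.1 quotes 6 and 8; with SDs that small, the same shift would raise the type I error further.

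Grouped as assigned, each arm mean falls by *ph*, so the expected difference is 0.

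Grouped as received, the MA group has 45(1−*p*) knees, none of them low-scoring. The FA group has 45(1+*p*) knees, of which 90*p* are low-scoring. Hence

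FA − MA = −2*ph*/(1+*p*).

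The type I error uses a normal approximation with SE = SD × √[1/(45(1−*p*)) + 1/(45(1+*p*))].

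| *p* | *h* | Shift (points) | Share of 12 points | Two-sided type I error, SD 22.9 to 20.3 |
|---|---|---|---|---|
| 5% | 10 | −2×0.05×10/1.05 = −0.95 | 8% | 0.054 to 0.056 |
| 10% | 20 | −2×0.10×20/1.10 = −3.6 | 30% | 0.12 to 0.14 |
| 20% | 20 | −2×0.20×20/1.20 = −6.7 | 56% | 0.27 to 0.33 |

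The negative sign means that this scenario works against FA. If the low-scoring knees were instead FA knees converted to MA, the shift would have the same size in favour of FA. The sign also reverses if converted MA knees have the better prognosis.

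**The case against.** The strongest reply is that this is a drafting slip in an analysis that is not primary. Reading (c) fits the surrounding sentences, and reading (b) leaves the ITT comparison intact. This stands to the extent that 6.3 cannot be said to have decided to move converted patients between arms. It does not remove the need for a correction, because an analyst who follows the sentence literally would move them.

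A second reply is that conversions should be rare. Sections 3.7 and 19.9 send knees that cannot be balanced within the limits to soft tissue release in both arms, and 19.9 says that the limits are always observed. This also stands. A reader might infer from the narrower control limits that hard-to-balance control knees will probably be converted to FA; the documents do not support that, since release is the specified response. Still, 6.3 itself provides for conversion in both directions.

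A third reply concerns form 19.8, where technique is recorded as "Mechanical Alignment OR Mechanical w/ Bony Release OR Functional Alignment". A reader might infer that three options for two arms make technique received impossible to establish. That goes too far. Two options are labelled mechanical and one functional, and 3.7 allows minor bony adjustment in the control arm. The form also records planned and final component angles, final limb alignment and releases, against which technique can be checked.

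**Conclusion.** Section 6.3 is wrong as written: it gives incompatible grouping rules, and on its literal reading the one analysis that could keep all patients as randomised becomes as-treated for converted knees. This conclusion rests on the text alone.

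The size of any bias is unknown. The shifts of 0.95 to 6.7 points depend wholly on assumed values of *p* and *h*, on one-way conversion of every low-scoring MA knee, and on SDs that the plan does not state. With few conversions the effect would be small.

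A reader might infer that the sentence favours FA and so inflates a superiority claim. The documents do not show this. The direction depends on which knees convert and which way, and the scenario worked above runs against FA. What can be said is that the bias may go either way and that grouping by randomised arm removes it.

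**What to change.** Replace the conversion sentence in 6.3 with:

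> Patients whose technique is converted intraoperatively are analysed in the arm to which they were randomised in every ITT analysis; an analysis by technique received is a sensitivity analysis only.

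Keep the existing commitment to document and publish conversions. The technique field on form 19.8 need not be replaced.

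The cost is one sentence, with no extra patients, visits or data, and the as-received comparison remains available as supportive. An as-randomised comparison is diluted by crossover: if the operation received makes a true 12-point difference and 10% of MA knees convert to FA, the expected difference is 12 × 0.90 = 10.8 points. That is the usual price of ITT and a reason to keep the as-received result as a labelled sensitivity analysis.
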